#### **Patient – Reported Outcomes:**

Eight Patient-Reported Outcome Measurement Information System (PROMIS) GI symptom scales have been developed and validated to capture the breadth and depth of GI symptoms experienced by people with a wide range of digestive disorders. In this study, only nausea and vomiting (4 items), diarrhea (6 items), and belly pain (5 items) symptom scales will be collected. The participants will be asked to complete the evaluation electronically from home or at site before the start of any procedures or tests, at the timepoints showed in the SoA ([Appendix D](#)). In case of early IMP discontinuation, the PROMIS GI symptom scales will be completed by the participant at the time of discontinuation and afterwards as normally planned.

The analysis of PROMIS GI symptoms scales v1 will be descriptive with no formal testing and conducted on the ITT population. Summary statistics of the raw scores and T-scores of GI symptom scales at scheduled visits will be provided by treatment group for each scale (nausea and vomiting, diarrhea, belly pain). The raw score for each scale is calculated as the arithmetic sum of all the individual item scores according to PROMIS GI symptoms scales v1 documentation. In case the participant does not answer every question (has missing data), the raw score can be approximately estimated according to following steps:

- Sum up all scores from the items that were answered
- Multiply the results obtained above by the total number of questions in that scale
- Divide the results obtained above by the number of items answered

The T-score will be calculated using the association table provided in the PROMIS GI symptoms scales v1 documentation between the raw score and T-Score. The T-score has been estimated using an item response theory graded response model (GRM) that includes a slope parameter that differs across items.

Plots will be also presented to illustrate trends over visits by treatment group for mean raw scores and mean T-scores for each scale. The mean raw scores and mean T-scores for each scale will be presented on the y-axis. Schedule visits will be presented on the x-axis.

#### **2.4.6 Analyses of pharmacokinetic variables**

Serum concentrations of efpeglenatide, pre-dose ( $C_{\text{trough}}$ ) and post-dose will be summarized (mean, SD, CV%, median, minimum, and maximum) over time and by treatment and by visit.

Serum concentrations of efpeglenatide, pre-dose ( $C_{\text{trough}}$ ) and post-dose, will be listed. Population PK analysis will be discussed in a separate analysis plan.

#### **2.4.7 Analyses of quality of life/health economics variables**

Not applicable.

### **2.5 DATA HANDLING CONVENTIONS**

#### **2.5.1 General conventions**

The following formulas will be used for computation of parameters.

##### ***Demographic formulas***

The participant's duration of diabetes (years) is calculated using the date of informed consent and the date of diabetes diagnosis.

If date of diabetes diagnosis is a complete date, then the duration of diabetes is  $(\text{date of informed consent} - \text{date of diabetes diagnosis} + 1) / 365.25$ . If date of diabetes diagnosis is a partial date:

- a) year and month are not missing, but day is missing, then  $\text{day} = 01$
- b) year is not missing, but month and date are both missing, then  $\text{month} = \text{January}$  and  $\text{day} = 01$ .

### ***Renal function formulas***

eGFR will be calculated using the 4-variable Modification of Diet in Renal Disease (MDRD-4) formula below (1):

- $$\text{eGFR (mL/min/1.73 m}^2\text{)} = 175 \times \text{serum creatinine (mg/dL)}^{-1.154} \times \text{Age (year)}^{-0.203} \times 1.212 \text{ [if black]} \times 0.742 \text{ [if female]}$$

#### **2.5.2 Data handling conventions for secondary efficacy variables**

No special data handling.

#### **2.5.3 Missing data**

For categorical variables, participants with missing data are not included in calculations of percentages unless otherwise specified. When relevant, the number of participants with missing data is presented.

Derived variables will be considered missing if any of the original variables required to calculate them are missing. For example, if either a baseline assessment or an endpoint assessment is missing for a participant, then change from baseline at endpoint will be missing. Depending upon the assessment, analyses may not include all participants in the analysis population, because certain participants in the intended population may have missing data.

#### ***Handling of computation of treatment duration if investigational medicinal product end of treatment date is missing***

For the calculation of the treatment duration, the date of the last dose of IMP is equal to the date of last administration reported on the treatment status case report form page. If this date is missing, the exposure duration should be left as missing.

In the definition of the on-treatment period, the date of the last dose of IMP is equal to the date of the last administration reported on the treatment status case report form page. If this date is missing, the date of the last IMP injection in the exposure page will be used for participants with at least 1 injection or the date of visit 3/randomization visit will be used for participants who were lost to follow-up after the initial dispensation of IMP.

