### 3 OBJECTIVES AND ENDPOINTS

**Table 1 - Objectives and endpoints**

Objectives	Endpoints
Primary	
To demonstrate the noninferiority of once-weekly injection of efpeglenatide 4 or 6 mg in comparison to once-weekly injection of dulaglutide 1.5 mg on HbA1c change from baseline to Week 56 in participants with T2DM inadequately controlled with metformin	
 
Change from baseline to Week 56 in HbA1c
 

Secondary	
To demonstrate the superiority of once-weekly injection of efpeglenatide 4 and 6 mg with once-weekly injection of dulaglutide 1.5 mg on glycemic control	
 
Change from baseline to Week 56 in fasting plasma glucose (FPG)
 
Number of participants with HbA1c <7.0% at Week 56
 

To demonstrate the superiority of once-weekly injection of efpeglenatide 4 and 6 mg with once-weekly injection of dulaglutide 1.5 mg on body weight	
 
Change from baseline to Week 56 in body weight
 

To evaluate the safety of once-weekly injection of efpeglenatide 4 and 6 mg and once-weekly injection of dulaglutide 1.5 mg	
 
Number of participants with at least one hypoglycemic event during treatment period
 
Number of hypoglycemic events per participant-year during treatment period
 
Number of participants with AEs (see Section 8.3)
 

Tertiary/exploratory	
To evaluate the immunogenicity of once-weekly injection of efpeglenatide 4 and 6 mg	
 
Number of participants by ADA status (positive/negative) at scheduled visits
 
Number of participants with treatment-induced ADAs (among the participants ADA negative or missing at baseline) during the study period
 
Number of participants with treatment-boosted ADAs (among the participants with ADA positive at baseline) during the study period
 
ADA titer at scheduled visits
 
Number of participants by ADA cross-reactivity to endogenous GLP-1 at scheduled visits
 
Number of participants by ADA cross-reactivity to endogenous glucagon at scheduled visits
 
Number of participants with ADAs directed against PEG linker of efpeglenatide at scheduled visits
 

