### **2.3.2 Safety population**

The safety population is defined as:

- Randomized population who received at least 1 dose or part of a dose of the IMP, analyzed according to the treatment actually received

In addition:

- Nonrandomized but treated participants will not be part of the safety population; however, their safety data will be presented separately
- Randomized participants for whom it is unclear whether they took the IMP will be included in the safety population as randomized according to their planned treatment

- For participants receiving 1 or more injections during the trial, the treatment group allocation for as-treated analysis will be included in the treatment group that they are exposed for longer duration. In case of tie, highest dose group of efpeglenatide will be used. When calculating the Dulaglutide treatment duration, the Dulaglutide 0.75 mg duration will be combined with Dulaglutide 1.5 mg
- Participants, who premature discontinued study treatment during the titration phase, will be summarized in their planned treatment group for as-treated analysis too.
- Randomized participants will be excluded from the safety population only if there is documented evidence (ie, all study dates recorded as no medication taken) that participants have not taken the study treatment. If a participant is dispensed IMP and is lost to follow-up without any documented evidence, the participant will be considered exposed.

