##### **2.4.3.1 Extent of investigational medicinal product exposure**

The extent of open-label IMP exposure will be assessed by cumulative exposure (patient years), duration (days), and category (weeks).

Duration of open-label IMP exposure is defined as last dose date – first dose date + 7, regardless of unplanned intermittent discontinuations (see [Section 2.5.3](#) for calculation in case of missing or incomplete data).

Duration of open-label IMP exposure will be summarized descriptively as a quantitative variable (number, mean, SD, median, minimum, and maximum). In addition, duration of treatment exposure will also be summarized categorically by numbers and percentages for each of the following categories and cumulatively according to these categories: 1 to 2 weeks, 3 to 4 weeks, 5 to 8 weeks, 9 to 12 weeks, 13 to 18 weeks, 19 to 24 weeks, 25 to 30 weeks, 31 to 43 weeks, 44 to 56 weeks, and >56 weeks. The duration of treatment exposure in weeks will be the duration (in days)/7, rounded to the nearest integer.

Duration of study will be summarized separately and analyzed descriptively as a quantitative variable (number, mean, SD, median, minimum, and maximum). The study duration is defined as date of completion or discontinuation – date of first open-label IMP + 1. If the date of first open-label IMP is missing, then the date of randomization will be used.

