### **2.4.5.2 Analysis of Hypoglycemia**

Treatment-emergent hypoglycemia events will be tabulated separately from the AEs.

Event frequency and incidence of hypoglycemia events will be summarized by treatment for all reported hypoglycemia and per type of hypoglycemic event described in [Section 2.1.4.6](#) (ie, severe, documented symptomatic, asymptomatic, probable symptomatic, relative) for safety population. Incidence of severe or documented symptomatic hypoglycemia events will be summarized by study period ( $\leq 4$  weeks (titration period),  $> 4$  weeks to  $\leq 8$  weeks,  $> 8$  weeks to  $\leq 30$  weeks,  $> 30$  weeks) and according to time of occurrence (nocturnal [ie, 00:00 to 05:59 am], daytime [ie, 06:00 am to 23:59]) for safety population. Documented hypoglycemia (symptomatic or asymptomatic) will be also evaluated for the more stringent plasma glucose threshold of  $< 54$  mg/dL (3.0 mmol/L), as well as for  $\geq 3.0$  and  $< 3.9$  mmol/L ( $\geq 54$  and  $< 70$  mg/dL). Frequency and percentage of participants with at least one hypoglycemia event will be summarized as well.

Event rate of hypoglycemia per participant year will be calculated by treatment using the total number of hypoglycemia events from all participants (denoted as n) divided by the total exposures from all participants expressed in years (ie, participant exposure in days divided by 365.25, denoted as t). Multiple events from an individual participant will all be counted. Event rates of hypoglycemia per participant year {all reported hypoglycemia, severe, documented symptomatic [ $< 54$  mg/dL ( $< 3.0$  mmol/L),  $\geq 54$  and  $< 70$  mg/dL ( $\geq 3.0$  and  $< 3.9$  mmol/L),  $\leq 70$  mg/dL ( $\leq 3.9$  mmol/L) respectively], asymptomatic, probable symptomatic, relative hypoglycemia} will be presented by treatment group during the 56-week on-treatment period.

The summary of frequency and event rate in participant years for severe or documented symptomatic hypoglycemia will be provided as appropriate by gender (Male, Female), age group ( $< 50$ ,  $\geq 50$  to  $< 65$ ,  $\geq 65$  to  $< 75$ ,  $\geq 75$  years), and race (Asian, Black or African American, White, Other).

A KM curve will also be provided by treatment group for the time to first severe or documented symptomatic hypoglycemia during the on-treatment period.

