### ***Handling of adverse events/hypoglycemia when date and time of first investigational medicinal product administration is missing***

When the date and time of the first open-label IMP administration is missing, all AEs/hypoglycemia that occurred on or after the day of randomization should be considered as TEAEs. The exposure duration should be kept as missing.

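### When a first- or last-dose date is missing, the SAP counts a participant's hypoglycemia events but drops the exposure time, so the per-participant-year rate has mismatched numerator and denominator

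*SAP*

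**What the plan says.** Protocol Table 1 lists "Number of hypoglycemic events per participant-year during treatment period" among the secondary safety endpoints. SAP 2.4.5.2 derives the rate in each arm as follows: "using the total number of hypoglycemia events from all participants (denoted as n) divided by the total exposures from all participants expressed in years". It adds that "Multiple events from an individual participant will all be counted".

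SAP 2.4.3.1 gives the exposure formula: "Duration of open-label IMP exposure is defined as last dose date – first dose date + 7". For missing or incomplete data it refers to SAP 2.5.3.

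In SAP 2.5.3, the paragraph on a missing end-of-treatment date sets two rules for a blank last-dose date on the treatment status page:

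- Exposure duration: "If this date is missing, the exposure duration should be left as missing".
- On-treatment period: "the date of the last IMP injection in the exposure page will be used for participants with at least 1 injection". For participants lost after the first dispensing, the Visit 3/randomization date is used.

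The SAP 2.5.3 paragraph on a missing first-administration date makes the same split. Adverse events and hypoglycemia from the day of randomization onward are treatment-emergent, but "The exposure duration should be kept as missing".

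SAP 2.3.2 keeps undocumented cases in the safety population: "If a participant is dispensed IMP and is lost to follow-up without any documented evidence, the participant will be considered exposed".

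**The concern.** A rate per participant-year needs events and time from the same people over the same span. With complete dates the SAP achieves this. The hypoglycemia window closes 7 days after the last injection (SAP 2.1.4), and exposure is the dosing span plus 7 days. When a date is missing, the window is rebuilt from a fallback date and the exposure is not, although the fallback date is in hand.

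The result is a denominator that is too small for its numerator. SAP 2.4.5.2 also asks for rates of severe or documented symptomatic hypoglycemia by gender, age group and race. In a small subgroup, one dropped exposure is a larger share of the person-time.

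**Working it through.** The documents state no hypoglycemia rate and no count of missing dates, so there is no planned figure to reproduce. I take the exposure in SAP 2.4.5.2 to be the duration defined in SAP 2.4.3.1, and a missing duration to contribute nothing to the sum.

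**Formula.** Let n be the events counted in an arm, T its person-time with the fallback dates applied, and t the part of T belonging to participants with a missing date.

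- Rate as written: n/(T - t)
- Rate with matched dates: n/T
- Ratio: T/(T - t) = 1/(1 - f), with f = t/T

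The ratio exceeds 1 whenever t > 0 and n > 0, whether or not the affected participants had events.

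**Inputs.** From the SAP: 300 participants per arm (1.3) and 56 weeks of treatment (1.4). Assumed: 3 or 15 participants affected (1% or 5%), each with w weeks of exposure, and 56 weeks for everyone else. With m affected, the inflation is m × w / [(300 - m) × 56]. The denominator is 297 × 56 = 16,632 weeks for m = 3 and 285 × 56 = 15,960 weeks for m = 15.

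| Affected | w = 1 | w = 12 | w = 28 | w = 50 | w = 56 |
|---|---|---|---|---|---|
| 3 (1%) | +0.02% | +0.2% | +0.5% | +0.9% | +1.0% |
| 15 (5%) | +0.1% | +1.1% | +2.6% | +4.7% | +5.3% |

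For example, 15 × 28 / 15,960 = 420/15,960 = 2.6%.

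**Which arm is affected more.** Take arm A with 15 affected at 4 weeks each: 60/15,960 = +0.4%. Take arm B with 6 affected at 45 weeks each: 270/(294 × 56) = 270/16,464 = +1.6%. Arm A has more missing dates and the smaller inflation. With equal underlying rates, the A/B ratio reads 1.0038/1.0164 = 0.988.

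**Lost straight after dispensing.** With the Visit 3 fallback, the event window closes 7 days after Visit 3, and matched exposure would be 0 + 7 = 7 days. That is 1/56 of a full 56-week exposure, so such participants change the rate very little.

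**Dropping affected participants from both n and t.** Assume 0.30 events per participant-year in everyone else, and 15 affected at 28 weeks, so f = 420/(15,960 + 420) = 0.0256.

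- If the affected have three times that rate, the matched rate is 0.30 + 0.60 × 0.0256 = 0.315. The rate as written is 0.315/(1 - 0.0256) = 0.324. Dropping them gives 0.300.
- If they have no events, the matched rate is 0.30 × (1 - 0.0256) = 0.292. Dropping them gives 0.300.

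Dropping removes the mismatch, but it matches the fallback-date rate only if the affected participants have the same event rate as the others.

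**The case against.** The best counter-argument is the opening of SAP 2.5.3. It says that a derived variable is missing if any input is missing, and that an analysis may therefore leave some participants out. If those with missing exposure left the rate entirely, numerator and denominator would match. But that rule is general, and nothing removes these participants' events from n. SAP 2.4.5.2 refers to all participants for both terms, and the first-dose paragraph keeps the events while leaving the exposure missing. At best the SAP allows two readings, and two programmers could produce different rates.

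Several limits do stand:

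- Missing dates may be rare. Protocol 7.1 and 7.1.1 require discontinuations to be documented, and Protocol 6.4 has the monitor check the administration data.
- SAP 2.4.5 describes the safety analysis as essentially descriptive. Hypoglycemia is not in the hierarchy of SAP 2.4.4.3, and no comparison of event rates is specified.
- The proportion with at least one event and the Kaplan-Meier curve do not use this denominator.

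A reader might infer that the arm with more loss to follow-up is always the more inflated. The documents do not support that. The trigger is a blank date, not loss as such, and the size depends on the person-time dropped, as the example of arms A and B shows. A reader might also infer inflation over the unknown true rate. The comparison here is only with the rate on the fallback dates, because the fallback also cuts off the events that can be counted.

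**Conclusion.** The inconsistency is real. Followed as written, SAP 2.5.3 and 2.4.5.2 inflate the rate by 1/(1 - f) relative to the rate using the SAP's own fallback dates. If 1% to 5% of an arm is affected, that ranges from almost nothing to about 1% to 5%, depending on how long those participants were exposed. These frequencies are assumptions, as are full 56-week exposures for everyone else. The trial was terminated early (SAP 2.3.1.2), so average exposure may be shorter and a given dropped exposure would then be a larger share.

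The arm that loses the larger share of its person-time is inflated more. No hypothesis test, type I error rate or power is affected. The point is worth correcting because it touches a listed secondary endpoint and the data needed are already collected.

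**What to change.** In SAP 2.5.3, with a cross-reference from 2.4.5.2, specify for the hypoglycemia rate denominator:

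- If the last-dose date on the treatment status page is missing, compute exposure with the fallback already used for the on-treatment period: the last injection on the exposure page, or else the Visit 3 date.
- If the first-dose date is missing, start exposure at the randomization date, which matches the event-counting rule. SAP 2.4.3.1 already uses that date for study duration.
- State that this overrides the general missing-data rule of SAP 2.5.3 for this rate.
- Report the number of affected participants per arm.

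The exposure summary in SAP 2.4.3.1 can keep its own rule. The cost is a few sentences and a small derivation change, with no new data. The downside is that a few durations will rest on the exposure page or on a nominal 7 days.

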#### ***Handling of medication missing/partial dates***

No imputation of medication start/end dates or times will be performed. If a medication date or time is missing or partially missing and it cannot be determined whether it was taken prior or concomitantly, it will be considered a prior, concomitant, and post-treatment medication.

For time to event (TTE) analysis, partial rescue medication dates will be imputed using the following rules:

- a) If year and month are not missing, but day is missing, then day = 15
- b) If year is not missing, but month and date are both missing, then month = June and day = 15.

Note: if it's possible that the partial date is within the on-treatment period, but the imputed date falls outside of the on-treatment period, then imputed date will be set to the nearest date inside the on-treatment period.

### ***Handling of adverse events/hypoglycemia with missing or partial date/time of onset***

Missing or partial AE/hypoglycemia onset dates and times will be imputed so that if the partial AE/hypoglycemia onset date/time information does not indicate that the AE/hypoglycemia started prior to treatment or after the on-treatment period, the AE/hypoglycemia will be classified as treatment-emergent. No imputation of AE end dates/times will be performed. These data imputations are for categorization purpose only and will not be used in listings. No imputation is planned for date/time of AE resolution.

### ***Handling of adverse events/hypoglycemia when date and time of first investigational medicinal product administration is missing***

When the date and time of the first open-label IMP administration is missing, all AEs/hypoglycemia that occurred on or after the day of randomization should be considered as TEAEs. The exposure duration should be kept as missing.

### ***Handling of missing assessment of relationship of adverse events to investigational medicinal product***

If the assessment of the relationship to IMP is missing, then the relationship to IMP has to be assumed and the AE considered as such in the frequency tables of possibly related AEs, but no imputation should be done at the data level.

### ***Handling of missing intensity of adverse events***

If the intensity is missing for 1 of the treatment-emergent occurrences of an AE, the maximal intensity on the remaining occurrences will be considered. If the intensity is missing for all the occurrences, a "missing" category will be added in the summary table.

### ***Handling of potentially clinically significant abnormalities***

If a participant has a missing Baseline, he or she will be grouped in the category "normal/missing at Baseline."

For PCSAs with 2 conditions, one based on a change from Baseline value or a normal range and the other on a threshold value, with the first condition being missing, the PCSA will be based only on the second condition.

For a PCSA defined on a threshold and/or a normal range, this PCSA will be derived using this threshold if the normal range is missing; eg, for eosinophils the PCSA is  $> 0.5$  GIGA/L or  $>ULN$  if  $ULN \geq 0.5$  GIGA/L. When ULN is missing, the value 0.5 should be used.

Measurements flagged as invalid by the laboratory will not be summarized or taken into account in the computation of PCSA values.

